## 5) Study Design

### a) Recruitment Methods

We will recruit 360 overweight and obese (BMI 24.5-40) subjects, and assuming a 20% dropout rate, this should lead to 240 completers. All subjects will be recruited among active shoppers at a predetermined Allegiance affiliated supermarket. Using strategies developed during the preliminary study, we will recruit shoppers by a cart display of weekly F&V samples and by listing study ads on store receipts, placing laminated posters by the cash register, and periodic email messages to shoppers. Subjects will be screened by a structured phone interview or by an in-person interview at the Allegiance affiliate supermarket.

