### 4) Resources Available to Conduct the Human Research

Enrollees will be 360 men and women ranging from 18 to 65 y.o., and estimating a dropout rate of 37.5%, this should lead to 225 completers. We are excluding those under 18 y.o. for two reasons: 1) There are relatively few customers under the age of 18 who are the primary shoppers for the household; and 2) we wish to recruit participants who are no longer growing in stature. The upper limit of 70 y.o. was used because older participants may experience non-volitional weight loss that is sometimes associated with aging. To reduce potential COVID exposure for high risk populations, we are reducing the age limit to 65. Similarly, the upper limit of BMI  $50 \text{ kg/m}^2$  was initially chosen because the degree of obesity  $>50 \text{ kg/m}^2$  is often associated with morbidity. However, to reduce risk to high-risk populations, the upper limit is reduced to  $40 \text{ kg/m}^2$ . We are limiting our sample to primary shoppers of the household who do  $\geq 30\%$  of total grocery shopping at their selected Allegiance affiliated supermarket, and regularly use their loyalty cards, to ensure that each participant generates sufficient purchasing data for analysis and that the intake data collected reflects the discount intervention's effects on purchasing. The exclusion criteria are designed to eliminate potential confounding factors that may affect purchasing or consumption behavior or body weight.

Participants will be carefully monitored using resources at Mt. Sinai Morningside/St. Luke's Clinical Research Unit (CRU). The unit director, [name] has agreed to provide both the space and resources necessary to conduct all of the minimally invasive medical procedures written into the protocol, [name], MD will also serve as the safety officer for this trial. [name] has experience conducting clinical research studies and a good understanding of obesity research. She will review the reports sent by the research coordinator, [name], MS, and will use the checklist attached to this document to determine whether there is any corrective action, trigger of an ad hoc review or stopping rule that should be communicated to the PI, the hospital IRB, and the NIH. In

	Protocol Name:	Multi-level supermarket discounts of fruits and vegetables on intake and health
	Principal Investigator:	[name]

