### c) Number of Subjects

We will recruit 360 overweight and obese (BMI 24.5-40) subjects, and estimating a 37.5% dropout rate, this should lead to 225 completers.

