### e) Endpoints

The primary endpoints will be at 40 and 56 weeks of participation. Once participants have started the intervention, data on compliance to the protocol will be collected at each visit by research staff and reviewed quarterly by the PI, the study statistician, and the safety officer. Compliance by participants will be evaluated by reviewing records. Data from subjects who show little or no purchasing during the first 8 weeks will be withdrawn from the study and from the analyses. If any serious issue arises, the study team will contact the individual to try to resolve any problems that exist. If the safety officer has concerns about whether compliance has reached a level that might inhibit the ability of the study to test its primary hypotheses, suggestions will be made for improving compliance.

An annual report will include a list and summary of adverse events. In addition, the annual report will address: (1) whether adverse event rates are consistent with pre-study assumptions, (2) reason for dropouts from the study, (3) whether all participants met entry criteria, (4) whether continuation of the

	Protocol Name:	Multi-level supermarket discounts of fruits and vegetables on intake and health
	Principal Investigator:	[name]
	Primary Contact Name/Contact Info:	[name] [contact] [name] [contact]
	Date Revised:	8/7/20
	Study Number:	HS#: 16-00407 GCO#: 16-1050

study is justified in order to collect additional data to accomplish the aims of the study, and (5) whether conditions are such that the study should be terminated prematurely. The annual report will be signed by the Safety Officer and will be forwarded to the IRB and to the NIH. A statement reflecting the results of the review will be sent to the NIH in the annual report (non-competing continuation). The adverse event form will be used by the study staff to report adverse events as they happen. The study statistician, the principal investigator, and the safety officer will review adverse event rates quarterly. Serious adverse events will be reported to the IRB, and if appropriate to NIH.

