Significant adverse events (SAEs) that are unanticipated or possibly related to the study intervention will be reported to the Safety Officer and PI as they happen, and to the IRB, and NIH within two weeks. Anticipated SAEs or those unrelated to the study intervention will be reported to the Safety Officer and PI as they happen, and to the IRB and NIH on a monthly basis.

We will monitor adverse effects in all participants; the safety officer, together with the PI, will alert the IRB and the NIH if a larger than reasonably expected adverse rate should occur. Other issues relating to stopping rules for this trial include:

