### **Limits of assumptions**

It is possible that excessive study dropouts and/or missing data by interim measurement time points will limit the value of data analysis of measurements. We have allowed for a 20% dropout rate, and a rate higher than 30% would be of concern. The dropout rate will be monitored semiannually.

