It is possible that excessive study dropouts and/or missing data by interim measurement time points will limit the value of data analysis of measurements. We have allowed for a 37.5% drop out rate, and a rate higher than 47.5% would be of concern. The dropout rate will be monitored semiannually.

- **Limits of rules**

We acknowledge that there are other situations that could occur that might warrant stopping the study, which would be included in "Other situations that have occurred since the last safety report that warrant discussion," to allow for communication of concerns to the study PI, statistician, and the safety officer.

*6. Where applicable, indicate dose selection procedures that will be used to minimize toxicity.*

N/A

*7. List any specialized grading system that will be used to evaluate adverse events (e.g., National Cancer Institute Common Toxicity Criteria).*

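### Section 5a's dropout rate and completer count disagree (360 at 20% gives 288, not 240), and the protocol carries two dropout levels of concern, 30% and 47.5%

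*Protocol*

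**What the plan says.** The protocol gives the expected number of completers in three places, each starting from 360 participants:

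- Section 5a, Recruitment Methods: "We will recruit 360 overweight and obese (BMI 24.5-40) subjects, and assuming a 20% dropout rate, this should lead to 240 completers".
- Section 5c, Number of Subjects: "We will recruit 360 overweight and obese (BMI 24.5-40) subjects, and estimating a 37.5% dropout rate, this should lead to 225 completers".
- Section 4, Resources: "estimating a dropout rate of 37.5%, this should lead to 225 completers".

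It gives the dropout rate that would cause concern in two places, each time in a paragraph headed Limits of assumptions:

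- Section 5e, Endpoints: "We have allowed for a 20% dropout rate, and a rate higher than 30% would be of concern".
- Data and Safety Monitoring Plan, item 5: "We have allowed for a 37.5% drop out rate, and a rate higher than 47.5% would be of concern".

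Both paragraphs are introduced by the same words: "Other issues relating to stopping rules for this trial include". Both also state: "The dropout rate will be monitored semiannually". The annual report, signed by the safety officer and sent to the IRB and NIH, has to cover the reasons for dropout and, as a separate topic, "whether conditions are such that the study should be terminated prematurely".

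The SAP gives no sample size, dropout rate or completer count.

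**The concern.** There are two faults. First, the numbers in section 5a do not agree with one another, and neither its dropout rate nor its completer count matches sections 4 and 5c. Second, the older-looking 20% assumption survives in section 5e and brings its own level of concern with it, while the monitoring plan uses a different pair of figures.

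The second fault matters more. Those who review dropout twice a year need to know what rate was expected and what rate is a warning. On the current text, a rate above 30% and up to 47.5% is a named concern in section 5e and not in the monitoring plan, and nothing says which paragraph prevails. The protocol's own planned rate lies in that interval, so section 5e would flag a trial that was going exactly as forecast.

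**Working it through.** **Inputs.** Enrolment 360 (sections 4, 5a, 5c). Dropout 20% with 240 completers (5a). Dropout 37.5% with 225 completers (4, 5c). Levels of concern 30% (5e) and 47.5% (monitoring plan).

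**Step 1: reproduce the completer counts.** Completers = N × (1 − d).

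- Section 5a: 360 × (1 − 0.20) = 288. The stated figure is 240, a shortfall of 48, which is too large to be rounding.
- Dropout implied by 240: 1 − 240/360 = 33.3%, or 120 dropouts.
- Working backwards from 240 completers at 20%: 240/0.80 = 300 recruited, not 360. The mistaken inflation 240 × 1.20 = 288 does not give 360 either.
- Sections 4 and 5c: 360 × (1 − 0.375) = 225, exactly as stated, and 225/0.625 = 360.

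Since 300 × 0.80 = 240, the figures in 5a may be left over from a recruitment target of 300. The documents do not say so.

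**Step 2: place the rates on one scale, out of 360.**

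| Rate | Where it comes from | Dropouts | Completers |
|---|---|---|---|
| 20% | 5a and 5e, allowed | 72 | 288 |
| 30% | 5e, level of concern | 108 | 252 |
| 33.3% | implied by 5a's 240 | 120 | 240 |
| 37.5% | 4, 5c and monitoring plan, allowed | 135 | 225 |
| 47.5% | monitoring plan, level of concern | 171 | 189 |

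The two levels differ by 171 − 108 = 63 participants. The planned 135 dropouts exceed the 30% level by 27. Even the 120 dropouts implied by 5a's own completer count exceed it, by 12.

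**Step 3: illustration.** Assume 360 independent participants, each dropping out with probability 0.375 by study end. With X ~ Binomial(360, 0.375), P(X > 108) = 0.998 and P(X > 171) = 0.00004. Under the plan's own assumption, one level would almost always be crossed and the other almost never.

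**Step 4: does it bear on power?** This cannot be checked, because the documents give no effect size, SD or power. For scale only, assume equal arms, 80% power, a two-sided 0.05 test and an unadjusted comparison of two arms among completers. The detectable difference in SD units is (1.960 + 0.842) × √(2/n):

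- n = 225/3 = 75: 0.46
- n = 240/3 = 80: 0.44
- n = 288/3 = 96: 0.40

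The two stated completer counts, 225 and 240, differ by about 3% on this scale (√(80/75) = 1.03).

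**The case against.** The strongest reply is that this is a leftover with little consequence. The section that exists to state the sample size (5c) is correct and agrees with section 4 and the monitoring plan, so a reader who looks there finds one consistent set: 360, 37.5%, 225, 47.5%. Enrolment and the analysis sets do not depend on the stray figures. No automatic action follows from either level. The documents list early termination as an annual-report topic of its own and do not tie it to a dropout rate. The SAP, dated 8-1-2023, is written in the past tense, so a correction now may serve the record more than the conduct of the trial.

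Much of this stands, and it limits the size of the point. There is no stated path from a dropout level to stopping, and the monitoring plan does not call rates up to 47.5% acceptable; it only declines to name them as a concern, and rates above 37.5% already exceed its allowance. The probability illustration also needs a denominator and a time point that the documents do not give. The plain fact that 37.5% exceeds 30% needs no model.

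What does not stand is the idea that the conflict resolves itself. Both versions are current text under one revision date, no order of precedence is given, and the SAP offers no figure to settle it.

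**Conclusion.** The point holds. Section 5a is wrong as written: its own rate gives 288 completers, its stated 240 needs 33.3% dropout, and neither matches the 37.5% and 225 given in sections 4 and 5c. The protocol also has two levels of concern for dropout, 30% and 47.5%, which are 63 participants apart with the planned rate between them. These conclusions rest only on the documents' own numbers and on taking each percentage as a share of the 360 enrolled.

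The consequence is a wrong forecast in 5a and dropout monitoring without a single benchmark. It is not shown to affect power, and it changes no analysis. It should be fixed because the figures govern what reviewers are told to expect and when they are told to worry.

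**What to change.** 1. In section 5a, replace the 20% dropout and 240 completers with 37.5% and 225. This is the only pair in the protocol that computes, and sections 4 and 5c already state it.
2. Reconcile the Limits of assumptions paragraph in section 5e with the one in the monitoring plan, so that one planned dropout rate and one level of concern appear throughout. For the level to signal a departure from plan, it has to lie above the planned rate; its value is for the sponsor to settle.

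The cost is the wording of two protocol sentences, one in 5a and one in 5e. Enrolment stays at 360, and visits, tests and analysis sets are unchanged. If dropout has already been reviewed, a note of which level was applied would complete the record.

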### b) Inclusion and Exclusion Criteria

#### Inclusion Criteria:

- Between 18 and 65 years of age
- BMI of 24.5 to 40 kg/m^2
- Accessible by telephone and email
- Self-identify as primary shopper for household
- Shops for > 30% of total grocery foods at a single Allegiance affiliated supermarket
- Consumes > 50% of food purchased at the Allegiance affiliated supermarket
- Weight stable (+/-5% in past 3 months)
- Agrees to the following study conditions:

	Protocol Name:	Multi-level supermarket discounts of fruits and vegetables on intake and health
	Principal Investigator:	[name]
	Primary Contact Name/Contact Info:	[name] [contact] [name] [contact]
	Date Revised:	8/7/20
	Study Number:	HS#: 16-00407 GCO#: 16-1050

- Be assigned to either one of the three study groups
- Use their newly issued reward cards each time they shop for 56 weeks
- Maintain 100% of their total grocery shopping at their designated supermarket for 56 weeks
- Not initiate a weight loss diet during the course of study
- Eat out or order take-out no more than five times per week
- Maintain non-smoking status throughout study (if non-smoker)
- Stop using their old loyalty card and use a new one we provide
- Not share new loyalty card with anyone else

Exclusion Criteria:

- Participating in other related research studies
- Plans to leave the area or take a vacation >4 weeks consecutively or more than 6 weeks total within the 56 -week period
- Currently enrolled in a weight loss program
- Engaging in more than 10 hrs of exercise and/or 8 hrs of weight training per week; participating in athletic competitions, marathons, or ‘bodybuilding’
- Restrictive eating habits (e.g., vegan, paleo, ketogenic, exclusively organic, gluten free, weight loss diet)
- Having surgery for obesity or taking weight-loss drugs
- Drinks excessively (3 or more drinks per day for men or 2 or more drinks per day for women)
- Change in smoking pattern in the previous 3 months (e.g., quit or began smoking in previous 3 months)
- Currently pregnant or plans to become pregnant within the next year
- Has given birth in the previous 12 months
- Currently breastfeeding or has breastfed in the previous 12 months
- Has a serious medical or psychiatric illness
  - Medical Diagnoses: uncontrolled diabetes, chronic organ failure (heart, lung, kidney, pancreas, etc.), inflammatory conditions (irritable bowel syndrome/disease, chronic malabsorptive diseases), hypertension >140/90 at the Screening Visit, HIV/AIDS, current serious STD, cancer (or < 5 years cancer free), major surgery within the previous 3 years, or other chronic disease which may impact weight status.
  - Psychiatric Diagnoses: severe depression, bipolar disorder, schizophrenia, dementia, eating disorder, or any other psychiatric condition which may impact typical intake of foods/fluids.
- Dependent on or abusing alcohol or other drugs, or not drug-free/sober for at least 6 months
- Currently receiving governmental discounts on fruits/vegetables (i.e., SNAP, WIC)
- Physical disability impacting safety of study procedures/tasks
- Has a chronic disease or takes medications that can put the individual at increased risk for a severe COVID-19 infection

Protocol Name:	Multi-level supermarket discounts of fruits and vegetables on intake and health
Principal Investigator:	[name]
Primary Contact Name/Contact Info:	[name] [contact] [name] [contact]
Date Revised:	8/7/20
Study Number:	HS#: 16-00407 GCO#: 16-1050

Several exclusions, such as serious disease, change in medications, or use of illicit drugs will help limit confounding influences on body weight and health outcomes. We will recruit weight-stable overweight and obese subjects, a group that generally reports low consumption of F&V. Increasing F&V intake in this overweight group is likely to lead to relatively greater health benefits and possible weight reduction than in those of normal weight, who are more likely to be consuming adequate F&V. The participant should be the main shopper who is already purchasing at least 30% of food at a given Allegiance affiliate supermarkets and is consuming at least 50% of the food purchased. We will include subjects who dine out (or order take-out) for lunch or dinner up to 5 times/wk. The primary food shopper and consumer will be the unit of analysis.

Review of the rate of subject accrual and adherence to inclusion/exclusion criteria will occur bimonthly during the recruitment period. This will assure that participants will meet eligibility criteria and ethnic diversity goals outlined in the grant application.

### c) Number of Subjects

We will recruit 360 overweight and obese (BMI 24.5-40) subjects, and estimating a 37.5% dropout rate, this should lead to 225 completers.

### d) Study Timelines

The total study period for each subject is 56 weeks. The study will commence with an 8-week baseline followed by a 32-week intervention and a 16-week follow-up period. Participants in the control group will receive a 16-week discount of 30% after they complete the follow up period (weeks 57 through 73).

### e) Endpoints

The primary endpoints will be at 40 and 56 weeks of participation. Once participants have started the intervention, data on compliance to the protocol will be collected at each visit by research staff and reviewed quarterly by the PI, the study statistician, and the safety officer. Compliance by participants will be evaluated by reviewing records. Data from subjects who show little or no purchasing during the first 8 weeks will be withdrawn from the study and from the analyses. If any serious issue arises, the study team will contact the individual to try to resolve any problems that exist. If the safety officer has concerns about whether compliance has reached a level that might inhibit the ability of the study to test its primary hypotheses, suggestions will be made for improving compliance.

An annual report will include a list and summary of adverse events. In addition, the annual report will address: (1) whether adverse event rates are consistent with pre-study assumptions, (2) reason for dropouts from the study, (3) whether all participants met entry criteria, (4) whether continuation of the

	Protocol Name:	Multi-level supermarket discounts of fruits and vegetables on intake and health
	Principal Investigator:	[name]
	Primary Contact Name/Contact Info:	[name] [contact] [name] [contact]
	Date Revised:	8/7/20
	Study Number:	HS#: 16-00407 GCO#: 16-1050

study is justified in order to collect additional data to accomplish the aims of the study, and (5) whether conditions are such that the study should be terminated prematurely. The annual report will be signed by the Safety Officer and will be forwarded to the IRB and to the NIH. A statement reflecting the results of the review will be sent to the NIH in the annual report (non-competing continuation). The adverse event form will be used by the study staff to report adverse events as they happen. The study statistician, the principal investigator, and the safety officer will review adverse event rates quarterly. Serious adverse events will be reported to the IRB, and if appropriate to NIH.

Significant adverse events (SAEs) that are unanticipated or possibly related to the study intervention will be reported to the Safety Officer and PI as they happen, and to the IRB, and NIH within two weeks. Anticipated SAEs or those unrelated to the study intervention will be reported to the Safety Officer and PI as they happen, and to the IRB and NIH on a monthly basis.

We will monitor adverse effects in all participants; the safety officer, together with the PI, will alert the IRB and the NIH if a larger than reasonably expected adverse rate should occur. Other issues relating to stopping rules for this trial include:

### **New information**

It is unlikely that new information will become available during this study that would necessitate stopping it.

### **Limits of assumptions**

It is possible that excessive study dropouts and/or missing data by interim measurement time points will limit the value of data analysis of measurements. We have allowed for a 20% dropout rate, and a rate higher than 30% would be of concern. The dropout rate will be monitored semiannually.

### **Limits of rules**

We acknowledge that there are other situations that could occur that might warrant stopping the study, which would be included in "Other situations that have occurred since the last safety report that warrant discussion," to allow for communication of concerns to the study PI, statistician, and the safety officer.

## **f) Procedures Involved in the Human Research**

**Baseline Period:** The 8 week baseline period and preceding pre-baseline period, will give subjects time to adjust to food shopping in one Allegiance affiliated supermarket. We will also monitor protocol compliance and spending level. The average amount spent on food shopping for the home per year per household (average 2.5 persons) for the NYC area is \$4066  $\pm$ 112 SEM [144]. Those not meeting a minimum of \$29/wk (~3 SD from the mean), or not reachable by phone for 24-h recalls, will be withdrawn from the study. 24-hour recalls will be obtained by phone calls in between visits. Under-

	Protocol Name:	Multi-level supermarket discounts of fruits and vegetables on intake and health
	Principal Investigator:	[name]
	Primary Contact Name/Contact Info:	[name] [contact] [name] [contact]
	Date Revised:	8/7/20
	Study Number:	HS#: 16-00407 GCO#: 16-1050

reporting of energy intake is common, and will be checked by comparing dietary recalls with estimated basal metabolic rates, via prediction equations. Deviations of reported energy intake from expected will be used as a covariate (compliance scale, 1-5) in the analyses.

**Intervention Period:** After the 8-wk baseline period, we will continue to monitor subjects' purchasing on a bimonthly basis to ensure that the card is being used. Subjects will be encouraged to contact us with any questions or concerns.

**Follow-up Period:** There will be a confidential exit interview with subjects at the end of the study (wk 56). The interview will follow after the final study payment, if possible, to decrease social desirability bias in responses. The interview will review compliance with the protocol, help detect any previous reporting bias, and obtain feedback about the subjects' experience. (**Appendix H**) (Duration: 10 min)

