### Specific Aims:

For the aims below, the first outcome (underlined) within each aim is primary, and the other outcomes are secondary.

**Primary Aim 1:** To investigate the effects of multi-level discounts on behavioral and health outcomes during the intervention period and their sustained effect during the follow-up period.

For greater price discounts ( $30\% > 15\% > 0\%$  group), we predict:

- a. *Purchasing Behaviors*
  - i. higher individual gross purchasing (i.e., price before discount) of F&V and non-caloric beverages
  - ii. reduced individual gross purchasing of less healthy, high energy dense (ED) highly processed foods (e.g., processed bakery items)
- b. *Consumption Behaviors*
  - i. higher individual F&V intake (g), the primary outcome measure (used to power the study), as assessed by 24-h dietary recalls and Brief Block Food Frequency Questionnaires (FFQ) (confirmed by biomarkers: plasma carotenoids and Vitamin C), as well as greater intake of non-caloric beverages
  - ii. decreased high energy-dense (ED) food intake (g), lower total fat intake (g), and lower daily energy intake (kcal)
- c. *Health Outcomes*
  - i. lower body weight (kg) and BMI ( $\text{kg}/\text{m}^2$ ), lower % body fat
  - ii. improved metabolic syndrome risk factors (fasting glucose, blood lipids, blood pressure)

	Protocol Name:	Multi-level supermarket discounts of fruits and vegetables on intake and health
	Principal Investigator:	[name]
	Primary Contact Name/Contact Info:	[name] [contact] [name] [contact]
	Date Revised:	8/7/20
	Study Number:	HS#: 16-00407 GCO#: 16-1050

**Primary Aim 2:** To investigate the effects of income as a moderator of outcome measures.

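### The $29/wk baseline spending floor is labelled about 3 SD below the mean but reproduces as the per-person mean minus 3 standard errors, so it is not an outlier rule for one-person households

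*Protocol*

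**What the plan says.** Protocol section 5f, Baseline Period, gives the source of the floor: "The average amount spent on food shopping for the home per year per household (average 2.5 persons) for the NYC area is" $4066, with a standard error of $112. It then states the rule: "Those not meeting a minimum of \$29/wk (~3 SD from the mean), or not reachable by phone for 24-h recalls, will be withdrawn from the" trial. No adjustment for household size is stated, and the text does not say whether $29 is meant per person or per household.

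Two other places deal with low purchasing, without a dollar figure. Section 5e (Endpoints) says: "Data from subjects who show little or no purchasing during the first 8 weeks will be withdrawn from the study and from the analyses". Section 6 (Withdrawal of Subjects) has a similar rule for little or no purchasing over eight weeks.

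Three other statements bear on the point:
- The inclusion criteria ask for prior use of the store, "Shops for > 30% of total grocery foods at a single Allegiance affiliated supermarket", and for agreement to "Maintain 100% of their total grocery shopping at their designated supermarket for 56 weeks".
- They also require agreement to "Eat out or order take-out no more than five times per week", so meals bought elsewhere may lower grocery spending.
- Primary Aim 2 is "To investigate the effects of income as a moderator of outcome measures".

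**The concern.** A cut-off three standard deviations below a mean should catch only extreme cases, here people who hardly shop at the store. That needs an SD of spending between households, and the protocol gives only a standard error, which measures how precisely the mean is known. A cut-off built from the standard error can fall close to the centre of the distribution.

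If so, a rule presented as removing outliers would remove ordinary low-volume shoppers, mostly people living alone. The sample would lean towards larger households and bigger baskets, enrolled participants would be lost, and a reader of the results would not see the selection: the SAP defines its ITT sample by having a post-randomization measurement and does not mention baseline spending withdrawals.

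**Working it through.** **Inputs** (all from protocol section 5f): mean $4066/yr per household; SEM $112/yr; average household 2.5 persons; floor $29/wk. The documents give no SD, no survey sample size, no one-person spending figure and no household-size distribution.

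**Weekly figures**
- Household mean: 4066/52 = $78.19/wk. SEM: 112/52 = $2.15/wk.
- Per-person mean: 78.19/2.5 = $31.28/wk.

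**Reproducing the $29**
- Household mean minus 3 SEM: (4066 − 336)/52 = $71.73/wk. Does not match.
- Per-person mean minus 3 SEM: (4066 − 336)/52/2.5 = $28.69/wk. Rounds to $29; 1.1% off.
- Household mean minus 3 true SDs: this needs SD = (78.19 − 29)/3 = $16.40/wk, or $853/yr. With the stated SEM that implies a survey of (16.40/2.15)² ≈ 58 households. The survey size is not given, so this reading cannot be checked.

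Only the second version gives $29 from the printed figures alone.

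**Where the floor sits**
- Against the 2.5-person household mean: 29/78.19 = 37%.
- Against the per-person mean: 29/31.28 = 93%, a gap of $2.28/wk.

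**Share of one-person households below $29** (normal model, all groceries bought at the store)

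Share = Φ((29 − mean)/SD). With no documented SD, I take the $16.40/wk that the 3 SD label would imply and scale it to one person in three ways, with the mean at $31.28:

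| SD for one person | z | Share below $29 |
|---|---|---|
| 16.40/2.5 = $6.56 | −0.347 | 36% |
| 16.40/√2.5 = $10.37 | −0.220 | 41% |
| 16.40 unscaled | −0.139 | 44% |

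One-person households may spend more than 1/2.5 of the household average. With CV (SD/mean) from 0.21 to 0.50:

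| One-person mean | Share below $29 |
|---|---|
| 1.25 × 31.28 = $39.10 | 11–30% |
| 1.5 × 31.28 = $46.92 | 3–22% |

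**Larger households for comparison** (mean proportional to size, same model)
- Two persons, mean $62.55: 0.5% at CV 0.21, where z = (29 − 62.55)/(0.21 × 62.55) = −2.55; 14% at CV 0.50, where z = −1.07.
- 2.5 persons, mean $78.19: 0.1% at CV 0.21; 10% at CV 0.50, where z = −1.26.

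At any given CV, the one-person share is higher in every scenario above. The size of the gap depends on the CV.

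**The case against.** **A minimum basket is defensible.** Section 4 says the shopping criteria exist so that each participant yields sufficient purchasing data, and the baseline period is meant to check compliance and spending. That stands as a reason for some screen. It does not support this figure or its label, and it does not explain why section 5f is stricter than sections 5e and 6.

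**The figure may already be per person.** The match at $28.69 suggests so, and it answers anyone who infers that a 2.5-person threshold was applied unscaled. It does not rescue the rule. The floor then lies three standard errors, not three SDs, below the one-person average, and it is still applied as one flat amount to every household.

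**A reader might infer a clash with the 30% entry criterion**, because 0.30 × 78.19 = $23.46/wk is under the floor. The documents answer this. The 30% describes shopping before enrolment; participants agree to do all grocery shopping at the designated store during the study, and section 5f gives the pre-baseline and baseline periods as time to adjust.

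**A reader might infer that Aim 2 is compromised.** Aim 2 concerns income, and no passage links income to grocery spending or household size. The exclusion of SNAP and WIC recipients limits the low-income end separately. A narrower income range is plausible, no more.

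**Balance between arms.** Participants learn their group at week 8. A floor applied to baseline data before then affects who is represented rather than how the arms compare. I accept that.

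**Conclusion.** The concern holds as an error of basis and label with a consequence for representation. The 3 SD description is unsupported. The figure reproduces from a standard error, and the resulting floor is 93% of average per-person spending. For one-person households it is not an outlier rule, and it goes beyond the other two low-purchasing rules.

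These statements need only the protocol's own figures. That the sponsor actually calculated $29 in this way is an inference from the numerical match.

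The share removed is an assumption. It is tempting to say that the floor removes a third or more of one-person households. That follows only if they spend about the per-person average with an SD of at least $5.29/wk (2.28/0.431, where 0.431 is the normal quantile for one third). At 1.25 to 1.5 times that average, the modelled range is 3–30%. The documents cannot settle which case applies.

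**What to change.** In section 5f, delete the statement that the floor is about 3 SD from the mean. Replace the flat dollar amount with a card-activity screen, for example scanned purchases in most baseline weeks, and use the same definition for little or no purchasing in sections 5e and 6. State how permitted vacation weeks count, since absences of up to four consecutive weeks are allowed.

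Do not rescale the floor to 29/2.5 = $11.60 per household member. If $29 is already per person, that divides by 2.5 twice. It would also raise the floor for larger households, to 3 × 11.60 = $34.80 for three people and 4 × 11.60 = $46.40 for four, and so withdraw some who are now retained.

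The cost is a few sentences in the protocol. The downside is that some low-volume shoppers with noisier purchasing data stay in.

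The SAP is dated 2023 and written in the past tense, so enrolment may be closed. In that case, report the number withdrawn for baseline spending, by income and, where recorded, household size. Limit generalisation and the Aim 2 conclusion to the households that remained.
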